6.10. Annualized Flare Rate

The annualized flare rate for each subject is defined as the number of flares observed during the treatment period divided by the flare exposure time in days multiplied by 365.25. Flare exposure time of a subject is defined as the difference in days between the last BILAG-2004 assessment date and the date of first dose + 1. For subjects who do not experience any flares for each of the SLE flare definitions, then the number of flares for that subject will be set to zero for each definition.

[figure not shown]
Annualized flare rate will be calculated for each definition of SLE flare.

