- Significant non-compliance with study procedures to a degree that would put the subject at risk for continued participation in the trial as determined by the Investigator or the Medical Monitor.

• Development of active neuropsychiatric SLE (excluding lupus headache) sufficiently severe to interfere with ability of the subject to provide ongoing informed consent.

• Investigator decision: Investigator believes it is in the best interest of the subject to discontinue treatment with study drug.

Subjects who prematurely discontinue treatment with study drug should have all procedures outlined in the EoT visit, as well as an unscheduled ECG, performed as soon as possible, and not later than the next scheduled visit.

To minimize missing data for efficacy and safety assessments, subjects who prematurely discontinue treatment, and who do not withdraw consent, should otherwise continue with their regular study visit schedule without receiving study drug. In subjects who are unable to continue their regularly scheduled visits, a follow-up phone call should occur approximately 8 weeks (corresponding to 5X half-life) after the last dose of study drug to determine the status of any ongoing AEs/SAEs or the occurrence of any new AEs/SAEs.

Discontinuation from the Study (Early Termination)

In addition to the criteria for discontinuing study drug summarized above, individual subjects may be discontinued from the study prematurely (i.e., prior to Day 197) for any of the following reasons:

- Subject decision / withdrawal of consent; subjects can request to be discontinued from participation in the study at any time for any reason
- Investigator decision: Investigator believes it is in the best interest of the subject to be withdrawn from the study

For subjects who withdraw from the study prematurely (i.e., prior to Day 197), the End of Study (EoS) evaluations should be completed if possible, preferably within 2 weeks of study drug discontinuation. In addition, a follow-up phone call should occur approximately 8 weeks (corresponding to 5X half-life) after the last dose of study drug to determine the status of any ongoing AEs/SAEs or the occurrence of any new AEs/SAEs.

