6.5. Day 197 (End of Study)

The EoS visit should be scheduled 4 weeks after the EoT visit (Day 169) and should include the following:

- Record AEs and concomitant medications
 - Photography of any oral mucocutaneous lesions reported as AEIs, if applicable
- Perform complete physical examination; obtain vital signs and weight
- Obtain ECG
- Using the provided kit, collect blood and urine samples for safety laboratory evaluations and clinical biomarkers of SLE
- Using the provided kit, collect blood samples for PK /ADA
- Perform urine pregnancy test for WOCBP using the provided kits
- Complete the SDI

NOTE: Additional procedures and/or documentation to support diagnosis of new damage, compared to Baseline, may be required (e.g., radiographic evidence to support diagnosis of avascular necrosis; photography to support new diagnosis of skin damage; other); refer to Procedures Manual

Perform Investigator disease activity assessments: BILAG 2004, SLEDAI-2K 30, PhGA, CLASI.

NOTE: Additional procedures are required to support activity in some organ systems (e.g., confirmation of pleural or pericardial effusion). Refer to Procedures Manual

- Obtain Subject's disease assessments: PtGA, SF-36, FACIT-F (13-item)
- Skin photography, if applicable

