3.1.2. Secondary Efficacy Endpoints

Secondary efficacy endpoints are provided below:

- Annualized flare rate by British Isles Lupus Assessment Group (BILAG)-2004 flare index through Day 169 all flares
- Time-to-first flare by BILAG-2004 flare index
- Achievement of Lupus Low Disease Activity State (LLDAS) at Day 169
- Change from baseline in Systemic Lupus Erythematosus Disease Activity Index 2000 (SLEDAI-2K) total score at Day 169
- Cumulative prednisone-equivalent dose use (total area under the curve of daily prednisone-equivalent dose) through Day 169
- Achievement of ≥50% reduction in Cutaneous Lupus Erythematosus Disease Area and Severity Index (CLASI) activity score at Day 169 in the subgroup of subjects with baseline CLASI activity score ≥8

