7.6. Analysis of Secondary Efficacy Endpoints

Unless otherwise stated, the mITT population will be the basis for analyses of all efficacy endpoints. These data will be analyzed through Week 24 (Day 169) for subjects who complete treatment and through the last assessment recorded \leq 28 days after treatment discontinuation for subjects who discontinue treatment early.

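### SAP 6.10 counts flares over Day 1 to 169 but does not cap exposure time, so a Day 197 BILAG can lower a subject's annualized flare rate by about 14%

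*SAP*

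**What the plan says.** The annualized flare rate is listed first among the secondary efficacy endpoints (SAP 3.1.2): "Annualized flare rate by British Isles Lupus Assessment Group (BILAG)-2004 flare index through Day 169 all flares".

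SAP 6.10 gives the derivation. The numerator and scaling are "the number of flares observed during the treatment period divided by the flare exposure time in days multiplied by 365.25". Exposure time is "the difference in days between the last BILAG-2004 assessment date and the date of first dose + 1". No upper day limit is attached to that last assessment.

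The treatment period is a calendar interval. Protocol 8.2.2.3 gives it as Day 1 to 169, and SAP 4.1 as up to 24 weeks from first dose. The End of Study visit (Protocol 6.5) comes four weeks after Day 169 and includes the instruction "Perform Investigator disease activity assessments: BILAG 2004". Subjects who stop drug early but do not withdraw consent "should otherwise continue with their regular study visit schedule without receiving study drug" (Protocol 4.3.2), so their BILAG assessments continue.

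Two other places bear on the interval:
- SAP 7.6 sets a general data cut for secondary efficacy endpoints: "These data will be analyzed through Week 24 (Day 169) for subjects who complete treatment and through the last assessment recorded" no later than 28 days after discontinuation for those who stop early.
- SAP 7.4.2 and Table 2 assign this endpoint a treatment-policy strategy, under which observed treatment-period data are used whether or not drug was stopped or rescue taken.

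**The concern.** A rate needs its events and its time at risk to cover the same interval. Here the count stops with the treatment period, while the time at risk, as worded, continues to whichever BILAG came last. For anyone seen at Day 197, about 28 days enter the denominator without any chance of contributing to the numerator. Anyone whose last BILAG is at or before Day 169 has no such excess.

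Two subjects with the same flare experience through Day 169 can therefore receive different rates only because one attended the final visit. SAP 7.6.2 analyzes the per-subject rates by analysis of variance, so the distortion passes directly into the arm means. At stake are the absolute level of the reported rates, the size of any difference on that scale and, if Day 197 attendance differs by arm, the comparison itself.

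**Working it through.** The documents give no numerical flare rate and no discontinuation rate, so there is no stated figure to reproduce. The check is on the derivation.

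**Inputs**
- Count interval: Day 1 to 169 (Protocol 8.2.2.3; SAP 4.1).
- Exposure: date of last BILAG minus date of first dose plus 1 (SAP 6.10). With first dose on Day 1, this equals the study day of the last BILAG.
- BILAG visits at Day 169 and Day 197, each with a window of ±3 days (Protocol Table 1).
- Assumptions: constant flare intensity, and assumed shares of subjects lacking a Day 197 BILAG.

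**Step 1. One completer with one flare.** Rate = flares / exposure days × 365.25.
- Exposure ending at Day 169: 1/169 × 365.25 = 2.16 per year.
- Exposure ending at Day 197: 1/197 × 365.25 = 1.85 per year.

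**Step 2. Size of the factor.** 169/197 = 0.858, or 14.2% lower. Across the visit windows the extremes are 166/200 = 0.830 and 172/194 = 0.887, or 17% to 11% lower.

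**Step 3. Effect on the comparison, with identical true rates in both arms.** A subject without a Day 197 BILAG has a factor of 1, because count and exposure end together. If a share q of an arm lacks that BILAG, the arm's factor is (1 − q) × 0.858 + q.

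| Share lacking Day 197 (arm A vs arm B, assumed) | Factor A | Factor B | Spurious ratio A/B |
|---|---|---|---|
| 10% vs 10% | 0.872 | 0.872 | 1.000 |
| 10% vs 20% | 0.872 | 0.886 | 0.984 |
| 10% vs 30% | 0.872 | 0.901 | 0.968 |

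The arm with better Day 197 attendance looks slightly better. With equal attendance the ratio is unaffected, and the difference in mean rates shrinks by the common factor.

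**Step 4. If the Day 169 cut in SAP 7.6 is applied to exposure time.** For completers the factor is 169/169 = 1.00 and the mismatch disappears.

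**Step 5. Early stoppers.** Under treatment policy with a calendar treatment period, visits after stopping and by Day 169 enter both count and exposure, so they cause no mismatch by themselves. The 28-day limit in 7.6 raises a separate problem. For a subject who stops on Day 85 and stays in the study, it ends the analyzed data at Day 85 + 28 = Day 113. It then discards up to 169 − 113 = 56 days of treatment-period follow-up that 7.4.2 and Table 2 say should be used.

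**The case against.** The strongest reply is that the plan already settles the interval. The endpoint is labelled "flare index through Day 169 all flares", Table 2 repeats that horizon, and SAP 7.6 cuts completers' secondary efficacy data at Day 169. SAP Table 4 also places assessments from Day 184 onward in a separate End of Study window. If 7.6 selects the data and 6.10 supplies the formula, the last BILAG for a completer is the Day 169 one and nothing is understated. Nothing in the SAP gives Section 6 precedence over Section 7. In addition, a factor common to all subjects scales the difference and its standard error together, and the trial was not sized for formal efficacy testing (SAP 4.2).

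Much of this stands. It shows the probable intent, and it rules out calling the understatement an established fact. It does not close the gap. SAP 6.10 is the only definition of exposure time, and 7.6 never mentions exposure time. Sections 6 and 7 also cannot be assumed to agree: for time to first flare, 6.9 censors at the EOT date while 7.6.3 censors at the last available BILAG. Nor can 7.6 be imported unchanged, because its 28-day limit contradicts the treatment-policy strategy for this same endpoint. Two programmers could follow this SAP faithfully and produce different rates.

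One limit on the check: a figure in SAP 6.10 is not visible in the text available here. If it contains a formula, it may fix the interval.

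**Conclusion.** The point holds as a drafting gap in the derivation of a secondary endpoint. Programmed literally, 6.10 lowers the rate by about 14% (11% to 17% across visit windows) for subjects with a Day 197 BILAG and leaves the others unchanged. Between-arm distortion arises only if attendance at that visit differs: about 2% for 10% versus 20% lacking it and about 3% for 10% versus 30%. These shares are assumptions. If the Day 169 cut is applied to exposure time, the effect for completers is zero.

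A reader might infer that early stoppers' rates are understated far more. If only on-drug flares were counted, a subject stopping at Day 85 and followed to Day 197 would have a factor of 85/197 = 0.43, and unequal stopping could then produce a sizeable false difference. The documents do not support that reading. They define the treatment period by calendar days and retain treatment-period data after drug is stopped, so post-stopping flares through Day 169 are counted. A reader might also take it as settled that Day 197 is in the denominator. The text allows this, but the endpoint label and 7.6 point the other way.

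**What to change.** Amend SAP 6.10 so that both terms use one interval:
- Count BILAG flares from first dose to the last BILAG on or before the Day 169 analysis visit, regardless of drug discontinuation.
- Divide by the days from first dose to that same BILAG date, keeping the existing plus-one convention.
- Exclude the Day 197 BILAG from both terms, and report flares between Day 169 and Day 197 separately.

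In SAP 7.6, state that the 28-day post-discontinuation cut does not apply to the annualized flare rate, so that the section agrees with 7.4.2 and Table 2. Changing 6.10 alone would leave it in conflict with 7.6.

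The cost is a few sentences and one derivation, and SAP Section 8 already provides for an SAP amendment. No additional data are needed. The downside is that reported absolute flare rates become somewhat higher than under the literal derivation, by up to 197/169 = 1.17 times for a subject seen at exactly Day 169 and Day 197.

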6.11. BILAG-2004 System Organ-Specific Response

For each system organ with A or B scores at baseline, treatment response is achieved if all of the following criteria are satisfied:

- Reduction from A at baseline to B, C or D or reduction from B at baseline to C or D
- No early discontinuation of study drug
- No use of restricted medications beyond the protocol-allowed threshold before assessment (see Section 6.21)

Response will not be calculated for system organ with no baseline score of A or B.

6.14. Lupus Low Disease Activity State

Lupus Low Disease Activity State [Franklyn, 2016] is binary state achieved if all the following criteria are satisfied:

- SLEDAI-2K total score ≤4, with no activity in major organ systems (renal, central nervous system, cardiopulmonary, vasculitis, fever) and no hemolytic anemia or gastrointestinal activity
- No new features of lupus disease activity compared with the previous assessment,
- PhGA \leq 1 on a 3-point scale
- Current prednisolone-equivalent dosage ≤7.5 mg/day
- Well-tolerated standard maintenance dosages of immunosuppressive drugs and approved biologics

6.15. SLEDAI-2K Total Score

Total score is defined as the sum of the weighted scores of each individual item within each organ system class.

6.17. Cutaneous Lupus Erythematosus Disease Area and Severity Index Activity Score

The CLASI activity score is calculated by adding the numeric values of the responses to items in the erythema, scale/hypertrophy categories, the mucous membrane involvement question, questions about acute hair loss and non-scarring alopecia. The scores for affected body parts are weighted equally regardless of surface area and number of lesions present. More severe manifestation within an area is scored higher then less severe manifestation.

6.18. 50% Improvement in CLASI Activity Score

A 50% reduction in CLASI activity score compared to baseline defined by meeting all of the following criteria:

• Achieve ≥50% reduction from baseline in CLASI activity score at Day 169

6.21. Restricted/Rescue Medications

During the Treatment Period, subjects treated with new concomitant medications or increased dose of the existing treatment will be considered non-responders (treatment failures) for assessments of SRI-X, BICLA, SLEDAI-2K Improvement, and 50% Improvement in CLASI activity score efficacy endpoints for visits after taking the restricted medication. Criteria for restricted/rescue medications include the following:

- Oral corticosteroids (prednisone, methylprednisolone, prednisolone, fludrocortisone acetate) can be taken during the study per the protocol criteria however the following would qualify the subject as a treatment failure:
 - Increase in dose from baseline of oral corticosteroids (burst) from Day 1 through Day 141 lasting more than 14 days (i.e., subject must taper back down to baseline dose level by Day 14 of the increase; for subjects not previously taking oral corticosteroids, taper must be down to 0 mg/day within 14 days); such a course also cannot be initiated more frequently than every 28 days
 - Dose greater than 40 mg prednisone/day (or equivalent)
 - Initiation of new oral corticosteroids or an increase in dose after Day 141
- Intramuscular corticosteroids can be taken during the study however, the following would qualify the subject as a treatment failure:
 - Intramuscular methylprednisolone dose greater than 160 mg administered at a single timepoint from Day 1 through Day 169
 - Intramuscular corticosteroids given at a frequency greater than 28 days
 - Initiation of new intramuscular corticosteroids or an increase in dose after Day 141

- Topical corticosteroids can be taken during the study however, the following would qualify the subject as a treatment failure
 - Increase in dose from baseline of topical corticosteroids (burst) from Day 1 through Day 141 lasting more than 14 days (i.e., subject must taper back down to baseline dose level by Day 14 of the increase; for subjects not previously taking topical corticosteroids, taper must be down to 0 mg/day within 14 days); such a course also cannot be initiated more frequently than every 28 days
 - Initiation of new topical corticosteroids or an increase in dose after Day 141
- Intravenous corticosteroids
- Increase in dose or addition of hydroxychloroquine or hydroxychloroquine-like drugs (hydroxychloroquine, hydroxychloroquine sulfate, chloroquine phosphate)
- Any new medication started during the study for SLE. The following exceptions are allowable:
 - Corticosteroid burst as specified above
 - Medication may be reduced or temporarily discontinued for safety reasons and then started again. This would not be considered a new medication
- Other restricted medications taken any time during the study:
 - Biologics (e.g., abatacept, anifrolumab, atacicept, belatacept, belimumab, obinutuzumab, ocrelizumab, rituximab, telitacicept)
 - Investigational agents

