8.2.2.3. Treating Increases in SLE Activity

The decision to treat increased SLE disease activity is based on the judgement of the Investigator. Increased disease activity should not be recorded as an AE; however, information regarding the organ system involved and the severity of disease activity leading to treatment should be captured in the disease assessments tools (e.g., BILAG 2004, SLEDAI-2K 30, PhGA) and also recorded as the indication for treatment with the concomitant medication. Increase in corticosteroids is treated separately from increase in, or addition of, other agents, as detailed below.

Burst and Taper of Corticosteroids

Prior to initiation of a burst of corticosteroids, all assessments should be completed that pertain to the visit at which the increased disease was recognized, if possible. If the increased disease was recognized between scheduled visits, then the subject should return to the clinic and all assessments listed for an unscheduled visit due to increased SLE activity (see §6.6.2) should be performed.

From Day 1 through Day 141, subjects with increased disease activity that require a temporary increase from the baseline oral corticosteroid dose may initiate either of the following:

- Oral corticosteroids administered up to a maximum dose of 40 mg prednisone/day (or equivalent) and tapered to the Day 1 dose by the end of the 14th day after initiation at the latest, or
- Intramuscular methylprednisolone up to a maximum of 160 mg administered at a single timepoint

The following additional guidelines apply:

• A course of oral or intramuscular corticosteroids cannot be initiated more frequently than every 28 days

If a subject requires initiation of a burst of corticosteroids after Day 141, or at a higher dose, or more frequently, or for longer than permitted, the subject should remain in the study for evaluation of safety and outcomes. Blinded study drug may be continued if not contraindicated in the judgement of the Investigator following discussion with, and agreement by, the Medical Monitor.

Increase or Addition of Hydroxychloroquine/Hydroxychloroquine-like Drugs and/or Immunosuppressants for Increased SLE Activity

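### SAP 6.21 applies the 28-day corticosteroid limit route by route, so an oral burst followed too soon by an intramuscular dose meets none of its oral or intramuscular failure bullets; the intramuscular frequency bullet is also worded in the wrong direction

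*SAP*

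**What the plan says.** **Protocol 8.2.2.3.** From Day 1 through Day 141, subjects with increased disease activity who "require a temporary increase from the baseline oral corticosteroid dose may initiate either of the following": an oral course (at most 40 mg prednisone-equivalent per day, back to the Day 1 dose within 14 days) or a single IM methylprednisolone dose of at most 160 mg. One limit follows for both: "A course of oral or intramuscular corticosteroids cannot be initiated more frequently than every 28 days". If a burst is given too often, the subject stays in the study. On dosing, the protocol says "Blinded study drug may be continued if not contraindicated in the judgement of the Investigator", and it adds that this requires discussion with, and agreement by, the Medical Monitor.

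**SAP 6.21.** The section opens with a default: "subjects treated with new concomitant medications or increased dose of the existing treatment will be considered non-responders (treatment failures". It then gives criteria in blocks by route.
- Oral: such drugs "can be taken during the study per the protocol criteria however the following would qualify the subject as a treatment failure". The first bullet covers bursts longer than 14 days and ends "such a course also cannot be initiated more frequently than every 28 days". The topical block repeats the same closing clause.
- IM: "Intramuscular corticosteroids can be taken during the study however, the following would qualify the subject as a treatment failure". The three bullets are a dose above 160 mg, "Intramuscular corticosteroids given at a frequency greater than 28 days", and new or increased IM use after Day 141.
- General item: starting any new drug for SLE is failure, with an exemption for a corticosteroid burst of the kind described earlier in the section.

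**Where it is used.** SAP 7.4.2 takes its definition of intercurrent event 2 (restricted or rescue medication) from 6.21. SAP Table 2 makes that event non-response for SRI-4 and BICLA. SAP 7.4.2 also drops SLEDAI-2K values recorded after it from the repeated-measures model.

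**The concern.** The protocol presents the two routes as alternatives for the same clinical need and limits them together. The SAP words its limits as if the routes were independent. A subject who moves from one route to the other inside 28 days has used more rescue than the protocol allows, yet may still count as a responder on both primary efficacy endpoints and keep later SLEDAI-2K values in the model.

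The SAP does not say that it means to depart from the protocol here. Section 8 says its analyses are consistent with the protocol, and section 6.11 points to 6.21 as the protocol's threshold for restricted medication. Because Protocol 10.1 gives the SAP precedence on analyses, the protocol limit does not fill the gap by default. If the text stays as it is, someone must decide how to score such cases while programming or reviewing data, when the rule should already be fixed.

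**Working it through.** The plan gives no figure for this point, so the check applies both documents' rules to example courses.

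**Inputs**
- Protocol 8.2.2.3: any oral or IM course starting less than 28 days after another breaches the limit.
- SAP 6.21, oral: failure if a burst exceeds 14 days, exceeds 40 mg/day, starts too soon after another oral burst, or starts after Day 141.
- SAP 6.21, IM: failure if a dose exceeds 160 mg, falls after Day 141, or meets the IM frequency bullet. That bullet is tested two ways: as presumably intended (gap under 28 days fails) and literally (gap over 28 days fails).
- Every oral burst below is itself permitted (at most 40 mg/day, at most 14 days), and every IM dose is 160 mg.

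| Courses | Gap in days | Protocol limit | SAP oral and IM bullets |
|---|---|---|---|
| Oral Day 85, IM Day 99 | 99 − 85 = 14 | breached | none met |
| Oral Day 127, IM Day 141 | 141 − 127 = 14 | breached | none met |
| IM Day 60, oral Day 75 | 75 − 60 = 15 | breached | no numeric bullet met; oral lead-in makes it ambiguous |
| Oral Day 60, oral Day 75 | 75 − 60 = 15 | breached | oral bullet met |
| IM Day 29, IM Day 43 | 43 − 29 = 14 | breached | met as intended; not met literally |
| IM Day 29, IM Day 71 | 71 − 29 = 42 | allowed | not met as intended; met literally |

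**Why the limits are by route.** The clause closing the oral bullet recurs word for word in the topical block, so each use refers to its own route. The IM bullet names IM only. The oral lead-in refers to the protocol criteria, which could bring the combined limit to bear on an oral burst that follows an IM dose. The IM lead-in has no such reference, so oral-then-IM is the clearer gap.

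**The general item.** It could fail a first IM dose as a newly started SLE drug. The exemption uses the word burst, which 6.21 applies only to oral and topical steroids. Against that, Protocol 8.2.2.3 lists IM methylprednisolone under its burst-and-taper heading, 6.21 says IM steroids may be used, and failing every new IM dose would leave the IM bullets little to do. The text supports both readings.

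**Effect at Day 169**
- Example: the IM dose on Day 99 falls 169 − 99 = 70 days before the endpoint.
- Compliant comparator: the same burst on Day 85 and the same IM dose on Day 113 (113 − 85 = 28 days, allowed) puts the dose 169 − 113 = 56 days before. The steroid total is the same and lies closer to the endpoint.
- Latest IM dose that escapes the bullets: Day 141, which is 169 − 141 = 28 days before, no closer than a single permitted IM dose on that day.
- Size of the IM dose: at most 160 mg × 1.25 (SAP Table 15) = 200 mg prednisone-equivalent.

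**Scale per subject.** SAP 4.1 says enrollment stopped at 76. Assuming an even split, 76 / 2 = 38 per arm, and one subject is 1/38 = 2.6 points. With 40 in the arm it is 1/40 = 2.5 points; with 36 it is 1/36 = 2.8 points.

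**The case against.** The strongest reply is that 6.21 is not silent. Its opening default makes new or increased treatment a failure, its list of criteria is introduced in non-exhaustive terms, and the general item can be read to catch a first IM dose given for SLE. This stands in part. A reader might infer that the oral-then-IM sequence meets no failure criterion anywhere in 6.21; the documents do not support that much. They support the narrower statement that it meets none of the oral or IM bullets and that the general item is unclear.

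A reader might also infer that treatment discontinuation never catches these subjects because study drug may continue. Continuation depends on the Medical Monitor's agreement, so some may stop and become non-responders as intercurrent event 1. Since stopping is not required, that event does not catch them reliably.

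The protocol sentence could be read per route, and it is a treatment rule that does not itself define responder failure. The combined reading is the more natural one, because the two routes are offered as alternatives and share a single limit. The remark in SAP 6.11 about the protocol threshold concerns organ-specific response, not SRI-4 or BICLA, so it shows general intent only.

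The IM frequency bullet may be only a slip that a programmer would correct from context. Even so, its literal text scores the wrong cases and should not be left to interpretation.

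Finally, efficacy is a secondary objective, the sample size was not derived for formal efficacy testing, and steroid use is reported elsewhere: cumulative prednisone-equivalent dose, medication summaries and listings, and deviation review. All of this limits the consequences. None of it changes a subject's responder status.

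**Conclusion.** The point holds as a defect in a scoring rule for both primary efficacy endpoints. The SAP's oral and IM bullets do not reproduce the protocol's combined 28-day limit, the general item does not clearly fill the gap, and the IM frequency bullet is wrong as literally worded.

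A reader might infer that response rates at Day 169 would be biased. The documents do not show that: a compliant subject can receive the same steroid total closer to Day 169. The documents do not give the number of subjects with mixed-route courses inside 28 days, and it is probably small. The 2.6 points per reclassified subject (2.5 to 2.8) is a scale that rests on the assumed arm size, and is not an estimate of effect. The conclusion also rests on reading the protocol limit across routes. The change is worth making because the rule feeds the primary endpoints and is cheap to correct; confidence is medium.

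**What to change.** Before unblinding, replace the oral and IM frequency wording in SAP 6.21 with one rule: *any oral burst or IM corticosteroid course given for SLE activity and started less than 28 days after the start of a previous oral burst or IM course given for SLE activity is treatment failure.* This removes the misdirected IM bullet and settles the IM-then-oral order.

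State also that the exemption in the general item on new SLE drugs covers oral and IM courses that meet the 6.21 limits. State that corticosteroids given for infusion reactions (which Protocol 8.1.1 allows) or for other non-SLE reasons fall outside this frequency rule. Leave the dose limits, the 14-day limit, the Day 141 cut-off and the topical rule unchanged.

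The cost is a short SAP amendment and one programming rule on concomitant-medication dates, routes and indications that are already collected. The downside is that a few more subjects may be scored as non-responders.
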